# 3. Background and justification for the design of the clinical investigation

## 3.1. Background

Out-of-Hospital Cardiac Arrest (OHCA) is a major health issue affecting approximately 380 000 persons in the U.S. and 270 000 in Europe each year.[1]. Presence of Pulseless Ventricular tachycardia (VT) or Ventricular Fibrillation (VF), amendable to defibrillation at first rhythm analysis is one of the strongest predictors of survival with survival rates up to 10 times higher compared to patients found in asystole or pulseless electrical activity.[2, 3] However, not all patients presenting with VT/VF will respond to defibrillation. The term "refractory ventricular fibrillation" is used for cardiac arrest patients who remain in VF despite 3 consecutive defibrillation shocks. Treatment recommendations for this condition include

[figure not shown]
Version No: 1.1

Date: 2024-10-27 19 (48)

administration of drugs such as Epinephrine and Amiodarone and continuous CPR, and in situations where available, consider transport during ongoing CPR to a facility capable of ECMO-assisted CPR.[4]

Importantly, survival of patients with VT/VF is inversely associated with the number of defibrillations required to terminate VT/VF.[5] Therefore, an intervention that could increase the rate of conversion from VT/VF into a perfusing rhythm earlier has the theoretical potential to increase survival.

Standard external defibrillation is provided by applying defibrillator pads in the anterio-lateral position (A-L) with the anterior pad placed to the right of the sternum, just below the clavicle and the lateral pad in the left mid-axillary line, approximately in level with a V6 ECG electrode. This position should be clear of any breast tissue, see fig A.[6]

An alternative pad placement is the so-called anterio-posterior position (A-P) where the anterior pad is placed on the left side of the sternum, below the clavicle, and the second posterior pad is placed on the back, to the left of the spine, below the left scapula, se fig B. Advantages with A-L position can be the possibility to perform defibrillation without adhesive defibrillation pads (not recommended during CPR since 2010), but it is also relatively ease to apply defibrillation pads during CPR, with no need to move the patient and application can be done while chest compressions are ongoing.

One advantage with A-P position is the theoretically closer proximity between pads (lower thoracic impedance) and that the pads are encircling the heart, i.e. more current is transmitted through the posterior parts of the heart. Disadvantages include the need to move

Version No: 1.1

Date: 2024-10-27 20 (48)

the patient to apply the posterior pad, interruptions in chest compressions during application, and no visual control over the posterior pad during chest compressions.

A-L pad placements has been compared to A-P placements in elective cardioversion of atrial fibrillation with conflicting results. However, more recent studies comparing A-L to A-P using modern biphasic rectilinear or truncated defibrillation waveforms have found A-L placement superior in this setting.[7]

An alternative defibrillation strategy with double sequential defibrillation includes the use of two defibrillators, one in the A-L position and one in the A-P position and defibrillation shocks in rapid sequence "Double Sequential Defibrillation" (DSD).

Double sequential defibrillation was described in 1994 to treat induced ventricular fibrillation during electro-physiology studies, that where refractory to standard defibrillation.[8] Observational studies and case reports of DSD has provided conflicting results. But usually DSD was used as an "last resort" when all other therapies had failed [9]. However, in 2022 the first and only randomized trial demonstrated increased survival with a strategy of either switching from A-L to A-P or from A-L to DSD in refractory VF (defined as VF at three consecutive rhythm analysis despite standard A-L defibrillation).

These results prompted the International Liason Committee on Resuscitation ILCOR to release a statement of treatment recommendation on DSD in March 6, 2023. It suggested that "either vector change or DSD may be considered for adults with cardiac arrest who remain in ventricular fibrillation or pulseless ventricular tachycardia despite three defibrillations (weak recommendation, low certainty of evidence)." Further, if DSD would be used it should be performed with a methodology similar to that described in the trial by Cheskes et al.

However, several questions remain. Knowledge gaps highlighted in the ILCOR statement included if the results from this one cluster randomized trial could be reproduced in any other setting. Further, since survival is inversely associated with the number of defibrillation shocks, if earlier application of DSD could lead to even higher survival for patients not in refractory VF has never been studied and finally no randomized trial on DSD has evaluated neurological function at 90 and 180 days or Health related quality of life.

# 3.2. Evaluation of results of prior testing, assessments and clinical investigations

As stated above, DSD has already been tested in a previous randomize controlled trial in humans and may according to international guidelines be considered in refractory VT/VF. The difference in this trial is to apply DSD after one failed defibrillation, before the VT/VF is considered refractory.

DSD with Corpuls3 is considered to be technically safe according to manufacturer, please see attached file "231130\_DSED\_eng\_Corpuls". Currently, corpuls3 and corpuls1 are tested for combability and technical safety when used for DSD.

Before those results are final and an application for a substantial modification is approved by the Swedish Ethical Review Authority and the Swedish Medical Products Agency no combination of corpuls3 and corpuls1 will be used in this trial.

Version No: 1.1

Date: 2024-10-27 21 (48)

#### 3.3. Evaluation of clinical data

Please see 3.1 above

# 4. Risks and clinical benefits of the investigational device and clinical investigation

## 4.1. Expected clinical benefits

Potential benefit with the DSD strategy includes:

The novel strategy of DSD might have a higher probability of terminating VT/VF and restore spontaneous circulation. Based on the results from one major previous trial there is a strong signal that DSD is superior to continuous standard defibrillation in refractory VT/VF in terms of saving more lives and neurological recovery. The clinical situation - to be in a cardiac arrest is highly time critical, and every minute that passes without restoration of spontaneous circulation is associated with lower survival. Every minute in delay without defibrillation and CPR raise mortality by 10%. Part of this outcome is due to irreversible brain damage that is caused by cerebral hypoperfusion during the cardiac arrest. The earlier VT/VF can be terminated, and spontaneous circulation be restored, the higher the probability of survival. We therefore believe that a DSD strategy a soon as possible can have a high potential to save more lives and this effect is dual effect since:

- a) A larger proportion of patients will have their VT/VF terminated and spontaneous circulation restored, e.g. higher survival
- b) The termination of VT/VF could occur sooner, leading to shorter duration of brain hypoperfusion and ischemia, e.g. better neurological function among survivors.

## 4.2. Anticipated adverse device effects

Possible adverse device effects with DSD compared to standard defibrillation include:

#### 1. Higher energy delivery

A DSD strategy includes a double amount of energy to be delivered for each defibrillation. This may result in injuries such as superficial burns on the skin.

## 2. Failure to deliver energy during defibrillation / or defibrillation malfunction

There may be a theoretical risk of potential damage to defibrillators due to no synchronized shocks.[10] There is a theoretical risk that synchronized defibrillation could lead to high voltage and cause damage to the defibrillators. This risk may be higher if the defibrillator pads from the two defibrillators are placed linear, as opposed to a 90-degree angle, and if defibrillation is synchronized. In this trial the second pair of defibrillation electrodes will be placed at an almost 90-degree angle and defibrillation will be performed sequential, meaning approximately one second delay between defibrillation using the two defibrillators, with one person pressing both defibrillators in sequence. In the trial by Cheskes et al. there were no reports of defibrillation malfunction in spite of more than 130 patients treated using DSD.

Version No: 1.1

Date: 2024-10-27 22 (48)

Also, in a recent survey on defibrillator damage during DSD use in clinical practice the rate of defibrillator damage seem to be exceedingly low.[11]

## 4.3. Risks associated with participation in the clinical investigation

Potential physical risks with the DSD strategy include:

1. The application of the second pair of defibrillation electrodes is associated with a short interruption in chest compression at the moment of placement of the posterior electrode. Long interruptions in chest compressions have been found to be associated with poorer outcome. However, short interruptions for ventilation have not been found to be worse than continuous chest compressions. In the trial by Cheskes et al. the application of the posterior electrode was done in a standardized way, using the interruption in chest compressions for ventilation and simultaneously move the patient and apply the posterior electrode. They could also report guideline compliant CPR Quality regardless of the treatment strategy the patient was randomized to (standard, Vector Change or DSD).[12] In order to minimize this risk there will be a mandatory training for all participating ambulance crew on how to synchronize posterior defibrillation electrode placements to pauses in ventilation. This extra moment should not take longer than 10-15 seconds

#### 4.4. Possible interactions with concomitant medical treatments

This is strictly a defibrillator manage/strategy study and no medication are involved. All other advance life support using adrenalin, amiodarone and other medical treatment follow standard routine for ACLS.

## 4.5. Steps to be taken to control or mitigate risks

- 1. Ambulance crew training. As mentioned above the main risk with the DSD strategy, as far as we know, is connected with the application of defibrillation electrodes and defibrillation. Therefore, all participating ambulance units must be trained and certified before participation in the trial. This in order to minimize risk of long interruptions in chest compressions and correct electrode placement.
- 2. Close monitoring will be done by the sponsor and the monitoring team on a case to case base. During the pilot study individual assessment and early feed-back of EMS intervention for every included patient can allow the sponsor for early detection of unanticipated adverse events. Please see also attached monitoring plan
- 3. Evaluation of defibrillators after each and every use. The corpuls3 performs a complete system check each time it is switched on. This internal automatic self-test checks the system components.

If error messages appear during automatic self-test, these are displayed in the

Version No: 1.1

Date: 2024-10-27 23 (48)

status line and listed in the event history. After each use of DSD, the defibrillators will be checked for malfunction by performing an automatic self-test to ensure functionality.

Furthermore, all defibrillators used in this DD study will be tested using a test-box and performing a test discharge will be performed once weekly during the study period (part of current routine) and as soon as possible after each DSD use.

- 4. Stepwise escalation of the pilot phase will be done in order to uncover unknown risks. In order to perform close monitoring of all included patients and feed-back from participating ambulance crew the trial will have an escalation strategy within the pilot study starting in two ambulance organizations and then escalate. The training protocol can be modified during the pilot study to mitigate potential risks. For all significant modifications, the Swedish medical product agency and the Swedish Ethical Review Authority will be notified. Please see also 9. Amendments to CIP.
- 5. Testing of combability of corpuls3 devices (performed) and for corpuls3 and corpuls1 (ongoing). Before those results are final and an application for a substantial modification is approved by the Swedish Ethical Review Authority and the Swedish Medical Products Agency no combination of corpuls3 and corpuls1 will be used in this trial.

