## 6.2. Endpoints

#### 6.2.1. Primary endpoints

**The main feasibility endpoint** is the proportion of included patients randomized before three EMS defibrillations.

In order to perform early DSD inclusion and randomization has to be quick, therefore the total number of EMS defibrillations prior to randomization was chosen as the main feasibility outcome. The goal is to perform randomization as soon as possible, however in clinical practice this can be challenging. A target of above 80% of included patients randomized before three EMS defibrillations is deemed acceptable. Other feasibility objectives will evaluate cross-over.

The main safety endpoints are related to CPR quality defined as chest compression fraction and any defibrillation malfunction defined as inability to defibrillate or any other defibrillator device deficiency (DD).

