#### Safety:

- Major adverse events (e.g. DD, skin burns)
- Chest compression fraction (hands off time during CPR, target > 80% in both groups)

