#### 8.1 Prehospital CRF1, Characteristics during the resuscitation phase

After completing the care of the patient, the study responsible EMS-unit will report a digital prehospital CRF. This is practically done by using and reading a study specific QR-code located on the back of the specific randomization envelope / sheet using a smart-phone. This will open a webpage automatic registration of time of registration and information to be filled in when opened.

Version No: 1.1

Date: 2024-10-27 33 (48)

The prehospital CRF will contain basic on-site information such as which ambulance that performed randomization, randomization study number, time and date of cardiac arrest, number of shocks prior to EMS arrival and number of shocks prior to randomization, treatment allocation, electrode placement for each defibrillation, number of defibrillations before DSD, ROSC and if the patients survived the event. Furthermore, if the patient has a known identity, personal id-number will be included to enable follow up. If the patients do not have a known identity a temporary identification number will be used.

The prehospital CRF allows for real-time monitoring of randomization and allows for early start of follow-up.

Other core resuscitation characteristics will later be reported and collected from the SRCR part 1 and ambulance charts. This registry data is standard and mandatory for all EMS personal to report and contains resuscitation and patient characteristics and reporting to the register is part of routine documentation.

ECG files from defibrillators. All data stored in the defibrillators after each use in the trial will be exported to a secure server and analyzed for defibrillation safety and CPR quality.

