## 14.1.6. **Device Deficiency**

A Device Deficiency (DD) is any inadequacy in the identity, quality, durability, reliability, safety or performance of an investigational device, including malfunction, use errors or inadequacy in information supplied by the manufacturer.

This includes detected errors at defibrillator self-test after each use.

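### Device deficiency is a main safety endpoint, but a prompt post-use test discharge is required only after DSD, and the self-test rule is worded inconsistently

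*Protocol*

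**What the plan says.** Section 6.2.1 of the Protocol makes the main safety endpoints chest compression fraction and "any defibrillation malfunction defined as inability to defibrillate or any other defibrillator device deficiency (DD"). The safety list that follows repeats this as "Major adverse events (e.g. DD, skin burns").

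How residual device faults are looked for is set out in section 4.5, item 3. Its heading is general: "Evaluation of defibrillators after each and every use". It then notes that "The corpuls3 performs a complete system check each time it is switched on", with errors listed in the event history. The sentence that prescribes the post-use check is narrower: "After each use of DSD, the defibrillators will be checked for malfunction by performing an automatic self-test to ensure functionality". The test-box discharge is to be done on all study defibrillators "once weekly during the study period (part of current routine) and as soon as possible after each DSD use".

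Section 14.1.6 defines a device deficiency and adds: "This includes detected errors at defibrillator self-test after each use". Section 14.2.2 uses the same wording for reporting. Neither limits it to DSD.

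Other routes apply to both arms. Under the prehospital CRF1 heading of section 8, "All data stored in the defibrillators after each use in the trial will be exported to a secure server" and analysed for defibrillation safety. Section 14.3 has every defibrillator file analysed for energy delivery at each shock, and CRF1 collects adverse events perceived by the crews.

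**The concern.** One route for finding a main safety endpoint is switched on by the treatment delivered. If DSD is given, the devices are test-discharged as soon as possible. If it is not, the device waits for the weekly discharge, by which time it may have been used on other patients. A fault found then cannot readily be assigned to the trial case. The trigger is DSD actually delivered, not the randomised arm: a DSD-randomised patient who receives no DSD falls outside it, and a control who crosses over falls inside it.

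Section 7.3 says that categorical outcomes are presented as differences in proportions. With a rare event, a single background fault found by DSD-triggered testing could colour the safety message carried into the main trial. The self-test wording adds a practical problem. Crews who follow the operative sentence of 4.5 would do no dedicated self-test after a control case, while 14.1.6 and 14.2.2 presume one.

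**Working it through.** The Protocol gives no power or sample size calculation (7.4), so there is no stated figure to reproduce. The allocation agrees with 6.3.3: 40 × 3/4 = 30 DSD and 40 × 1/4 = 10 standard.

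**Step 1: routes of detection**

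| Route | After DSD | After a use without DSD |
|---|---|---|
| File export and energy-delivery analysis (CRF1 section, 14.3) | yes | yes |
| Adverse events perceived by crews, CRF1 (14.3) | yes | yes |
| Automatic check at switch-on (4.5) | yes | yes |
| Weekly test discharge (4.5) | yes | yes |
| Dedicated post-use self-test | yes | contradictory: no by the operative sentence of 4.5; yes by its heading, 14.1.6 and 14.2.2 |
| Prompt post-use test discharge | yes | not required anywhere |

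Only the last row is a clear asymmetry. A fault that the self-test can detect would show at the next switch-on in either arm. What remains is a fault visible only on discharge.

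**Step 2: size**

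Assumptions: a background fault rate *q* per device, unrelated to DSD; two devices per DSD case and one per control; all 30 DSD patients receive DSD. The Protocol expects device deficiency in fewer than 1 in 100 (14.3), so *q* = 1% is the top of its own range. *q* = 3% is a stress value.

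- Device-uses: 30 × 2 = 60 against 10 × 1 = 10.
- Expected faults in the DSD arm: 60 × 0.01 = 0.6; 60 × 0.03 = 1.8.
- Expected faults in the control arm if all are detected: 10 × 0.01 = 0.1; 10 × 0.03 = 0.3.

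The most that unequal testing can hide among controls is therefore 0.1 to 0.3 events. The rest of the gap between arms comes from the number of devices.

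**Step 3: effect on the difference in proportions**

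Per patient at *q* = 1%, a DSD case has probability 1 − 0.99² = 0.0199 of at least one fault. A control has 0.01 × *s*, where *s* is the share of control faults detected. The Protocol does not give *s*, so a range is shown.

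| *s* | Control | Difference |
|---|---|---|
| 100% | 0.0100 | 1.0 point |
| 75% | 0.0075 | 1.2 points |
| 50% | 0.0050 | 1.5 points |
| 0% | 0 | 2.0 points |

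The difference is already 1.0 point with equal detection, because a DSD case uses two devices. Unequal detection adds at most another 1.0 point.

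**Step 4: against sampling error**

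With zero events, the exact two-sided 95% upper limit is 1 − 0.025^(1/n): 11.6% for n = 30 and 30.8% for n = 10. Sampling error is far larger than the detection effect.

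**The case against.** The case against runs as follows.

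- **The core of the endpoint is ascertained equally.** Inability to defibrillate is found from the defibrillator files, which are exported and analysed in both arms. This stands, and it confines the point to faults left in a device after the case.
- **The self-test is not clearly limited to DSD.** A reader of the operative sentence in 4.5 might infer that control devices get no post-use self-test. The heading of the same item, the switch-on check, and sections 14.1.6 and 14.2.2 do not support that. The self-test issue is a contradiction to reconcile, not a demonstrated asymmetry.
- **The extra discharge is a targeted precaution.** Section 4.2 places the device-damage risk in the use of two defibrillators, so checking promptly after DSD is reasonable. That explains the rule as risk control. It does not make it an even-handed way of collecting an endpoint.
- **The study is a pilot without hypothesis testing (7.4), focused on the intervention (6.3.3).** Section 7.3 is generic and does not name device deficiency as a compared outcome. This stands and limits the consequence.
- **Details may sit in the monitoring plan, which is not shown.** Possible, but the Protocol text would still disagree with itself.

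A reader might also set 60 promptly tested device-uses against none and take 0.6 v 0, or 1.8 v 0, expected faults as the size of the bias. That is not supported. Most of the contrast is 60 v 10 device-uses, which equal testing leaves unchanged, and the zero ignores the weekly discharge of all study defibrillators.

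**Conclusion.** The point holds in a narrow form. A prompt test discharge, one route to a main safety endpoint, depends on whether DSD was delivered, and no section requires it after other trial uses. A fault visible only on discharge is then found later and is harder to attribute. Separately, section 4.5 item 3 disagrees with its own heading and with 14.1.6 and 14.2.2 on when the self-test is done.

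The expected size is small: at most 0.1 to 0.3 control events at assumed per-device fault rates of 1% to 3%, and at most 1.0 percentage point on the difference in proportions at 1%. These are upper bounds, since they suppose that no control fault is found by any other route.

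It would go too far to conclude that controls provide no comparator for device faults. The weekly discharge would still find a persistent fault; what is lacking is a like-for-like comparator for faults found at prompt post-use discharge. Nor would the fix make 10 controls informative about a rare event. The change is worth making because it gives both arms the same checks on a main safety endpoint at trivial cost.

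**What to change.** Reconcile section 4.5 item 3 with 14.1.6 and 14.2.2. One sentence would do: every study defibrillator used on a randomised patient, in either arm and whether or not DSD was delivered, is self-tested and test-discharged as soon as possible after that use.

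In reporting, list deficiencies found at post-use testing separately from those that occurred during resuscitation. Give the number of device-uses as a denominator beside the per-patient count, because a DSD case uses two devices and a control case one.

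The cost is about 10 extra device checks for controls, plus those for DSD-randomised patients who receive no DSD. For illustration, if 80% of the 30 received DSD (the boundary of the synopsis target), 30 − 24 = 6 patients would not, adding 6 to 12 checks at one or two devices each. The number could be higher if VT/VF often ends before the next rhythm analysis. The test equipment is already in weekly use.
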